The calculation of sample size was based on the question: "Which of the applied caries treatment methods will have the least frequency of complication occurrences, treating severe early childhood caries in children from the ages of 2 to 6 years-old?" Since we will compare proportions in six groups, in the sample size calculation we used formulas, which are shown in Fig 1 (Shao, Chow and Wang, 2003), calculating that the planned number of various proportions for comparison will be 9.

From previous studies it is known that conventionally treating early childhood tooth caries, the frequency of complications is 10% (Innes *et al.*, 2013), but, examining clinical cards at RSU's Institute of Stomatology Children's Dentistry department, the frequency of complications for children that are waiting in line for treatment with general anaesthesia and who receive no additional treatment, is approximately 30%, therefore in the study's treatment groups we expect that the frequency of complications will be no greater than 10%, but in the placebo groups - 30%. From the calculations in the formulas above, we calculated, that for the study we need 49 children in each group, to ascertain the difference in complication proportions between 30% un 10% with α error 0.05 and with a study capacity of 80%. Together 294 children are necessary but, calculating possible losses during the observation time, it is planned to involve 70 children in each group, therefore, 420 in six groups.

$$n = (p_A(1 - p_A) + p_B(1 - p_B)) \left(\frac{z_{1-\alpha/(2\tau)} + z_{1-\beta}}{p_A - p_B} \right)^2$$

$$1 - \beta = \Phi(z - z_{1-\alpha/(2\tau)}) + \Phi(-z - z_{1-\alpha/(2\tau)}) \quad , \quad z = \frac{p_A - p_B}{\sqrt{\frac{p_A(1-p_A)}{n} + \frac{p_B(1-p_B)}{n}}}$$

Fig 1. Formulas to calculate the sample size. n = the sample size (for one comparison, therefore two equivalent groups); Φ = standard normal allocation function; α = I type error; τ = number of comparisons; β = II type error; $1-\beta$ = study capacity.

Randomization, allocation and blinding

Flow chart of research methodology is shown in Fig 2. If the patient fulfills the inclusion criteria, their parents (caregiver) will be offered the opportunity to participate in the study. The objective of the study will be explained both verbally and in writing, as well as the expected results and side effects of the treatments:

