1. The first placebo group – placebo varnish application twice with a six-month interval and a recommendation to brush teeth with a toothpaste containing fluoride (F content of at least 1000 ppm);
2. The second placebo group – placebo varnish application four times with a week's interval and a recommendation to brush teeth with a toothpaste containing fluoride (F content of at least 1000 ppm);
3. The first SDF group – Riva Star SDF (35-40% silver fluoride, 15-20% ammonium) application twice with a six-month interval and a recommendation to brush teeth with a toothpaste containing fluoride (F content of at least 1000 ppm);
4. The second SDF group - Riva Star SDF application four times with a week's interval and a recommendation to brush teeth with a toothpaste containing fluoride (F content of at least 1000 ppm);
5. The first Tiefenfluoride group – Tiefenfluoride (0,4% $\text{CuSiF}_6 \times 6 \text{H}_2\text{O}$, 10,9% $\text{MgSiF}_6 \times 6 \text{H}_2\text{O}$, 0,1% NaF, 9,6% $\text{Ca}(\text{OH})_2$) application twice with a six month interval and a recommendation to brush teeth with a toothpaste containing fluoride (F content of at least 1000 ppm);
6. The second Tiefenfluorid group - Tiefenfluorid application four times with a week's interval and a recommendation to brush teeth with a toothpaste containing fluoride (F content of at least 1000 ppm);

The goal of the treatment is to stop the progress of the existing damage progress and avert the formation of new damage; caries tissue removal will not be performed; the products will be applied to dried teeth.

For ethical reasons, the negative control group will not be used – in each of the study’s groups the parents (direct caregivers) will be given advice about tooth cleaning and diet, using motivational intervention principles and recommending brushing teeth with toothpaste that contains fluoride (at least 1000 ppm), which is defined as non-restorative caries treatment and which has also proven its effectiveness in stopping caries damage.

Outcome variables

Patients will be examined at the baseline and at 12 months.

The patient’s primary examination will determine the following parameters:

- 1) general information about the child (birth date, gender, medical health history);
- 2) hygiene and dietary habits (frequency of brushing teeth; are teeth cleaned by the child or by parents; the fluoride concentration in toothpaste);
- 3) plaque (visible/invisible);

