D6.2 Conference abstracts.

D6.3 Publication about the effectiveness of SDF and Tiefenfluorid treatment in preschool children with S-ECC (to be published in Caries Research (impact factor: 2.188) or in BMC Oral Health (impact factor: 1.602).

D6.4 Publication about the effectiveness of fluoride treatment according to the type of carious lesion in deciduous dentition (to be published in the International Journal of Paediatric Dentistry (impact factor: 2.18) or in European archives of paediatric dentistry: official journal of the European Academy of Paediatric Dentistry (impact factor: 1.48).

D6.5 Evidence-based recommendations and economic evaluation report for national policymakers.

Milestones of WP6

MS6.1 Meeting with Communication Department and IT department of RSU.

MS6.2 Scientific conferences.

MS6.3 Meeting with policymakers.

Gantt chart

The workflow in each work packages and relevant deliveries are illustrated in the Gantt chart (Fig 4.).

[figure not shown]

Fig 4. The Gantt chart of the clinical trial.

Risks

1. Research achievability risks
 - a. Number of patients recruited less than expected - sample size calculation was estimated using conservative assumptions. The expected difference in the prevalence of severe caries complications in different treatment groups and the placebo group is expected to be 20% (10% complication rate for treatment groups and 30% for placebo). From previous studies, the expected prevalence in treatment groups could be even less, meaning the observed difference would be greater. In such a case, statistical power can be achieved even with a lower number of patients.
 - b. Loss of follow-up – we plan to include 70 patients in every group in order to ensure that there are still at least 49 in every group at the end of the project (we assume the potential loss of follow-up examinations to be 30%, which we consider to be sufficient).
2. Research methodology risks

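### The 30% placebo rate comes from children without the advice and toothpaste recommendation every trial arm gets, and Risks 1a calls the assumptions conservative by looking only at the treatment rate

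*Protocol*

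**What the plan says.** **Placebo rate (Protocol, Sample size calculation).** The 30% comes from the department's clinic cards for children awaiting treatment under general anaesthesia "who receive no additional treatment, is approximately 30" per cent. It is then assigned to the placebo groups: "we expect that the frequency of complications will be no greater than 10%, but in the placebo groups - 30" per cent.

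**Active rate (same section).** The 10% is introduced from previous studies: "conventionally treating early childhood tooth caries, the frequency of complications is 10" per cent.

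**Care in the placebo arms (Protocol, Interventions).** An untreated comparator is ruled out: "For ethical reasons, the negative control group will not be used". Instead, "in each of the study’s groups the parents (direct caregivers) will be given advice about tooth cleaning and diet, using motivational intervention principles", together with a recommendation to use toothpaste of at least 1000 ppm fluoride. The Protocol describes this as care "which is defined as non-restorative caries treatment and which has also proven its effectiveness in stopping caries damage".

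**Reassurance (Protocol, Risks, 1a).** On possible under-recruitment, the text says that the "sample size calculation was estimated using conservative assumptions". The reason given is that the treatment-group rate might fall below 10%, in which case "statistical power can be achieved even with a lower number of patients".

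**The concern.** The control rate describes children without the extra care that every trial arm receives, and the Protocol credits that care with an effect on caries. If some of that effect carries over to complications, the placebo arms will have fewer than 30% events and the difference from the active arms may be smaller than 20 points. The sample size section neither mentions this nor allows for it.

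Risks 1a then looks at one side only. It considers a lower treatment rate, which would help power, and not a lower placebo rate, which would hurt it. That paragraph is the Protocol's answer to slow recruitment, so its optimism could affect how a shortfall is handled.

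**Working it through.** **Inputs (Sample size calculation and Fig 1).** Placebo rate pA = 0.30, active rate pB = 0.10, alpha = 0.05 two-sided, tau = 9 comparisons, power 80%. Stated result: 49 per group, raised to 70 for 30% loss (49 / 0.70 = 70). Quantiles: z(1 − 0.05/18) = 2.773, z(0.80) = 0.842, and z(0.975) = 1.960 with no multiplicity correction.

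**Step 1: the plan's own figure.**

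n = [pA(1 − pA) + pB(1 − pB)] × [(2.773 + 0.842) / (pA − pB)]²
= (0.21 + 0.09) × (3.615 / 0.20)² = 97.99, so 98 per group.

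The stated 49 is not reproduced. It is half of 98, which suggests that the formula's n was read as the total for two groups, though the document does not say so. A one-sided pooled test with no multiplicity correction also gives 49, but that contradicts the printed formula and the nine comparisons.

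Power from the second formula in Fig 1, at 30% vs 10%:
- 98 per group: z = 0.20 / √(0.30/98) = 3.615; Φ(3.615 − 2.773) = 80%.
- 49 per group: z = 0.20 / √(0.30/49) = 2.556; Φ(2.556 − 2.773) = 41%.
- 49 per group with tau = 1: Φ(2.556 − 1.960) = 72%.

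The fall from 80% to 41% therefore owes nothing to the placebo rate. To isolate the rate question, step 2 uses 98 per group, where the plan's own assumptions do give 80%.

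**Step 2: effect of the rates, 98 per group, tau = 9.** The document gives no rate for children who receive the advice and toothpaste recommendation. Every row after the first is an assumption.

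| Placebo | Active | What is assumed | Power |
|---|---|---|---|
| 30% | 10% | as planned | 80% |
| 25% | 10% | only placebo falls | 52% |
| 25% | 8.3% | risk ratio kept at one third | 67% |
| 20% | 6.7% | risk ratio kept at one third | 51% |
| 25% | 5% | 20-point gap kept | 91% |

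For example, at 25% vs 10%: z = 0.15 / √(0.2775/98) = 2.819, and Φ(2.819 − 2.773) = 52%. At a 25% placebo rate, an active rate near 6.7% would leave power at about 80%. The direction of the change therefore depends on the active rate as well.

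**Step 3: the claim that fewer patients could suffice.** Keep placebo at 30% and halve the active rate to 5%:

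n = (0.21 + 0.0475) × (3.615 / 0.25)² = 53.8, so 54 per group. With 49 per group, power is 75%.

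Halving the active rate is not enough for 49 completers under the plan's formula. The active rate would have to be about 4% or lower (n = 48.01 at 4%, so 49).

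**Step 4: two-way table for 49 completers per group.** Each cell gives power with tau = 9, then with no multiplicity correction.

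| Placebo | Active 10% | Active 8% | Active 5% |
|---|---|---|---|
| 30% | 41.4% / 72.4% | 54.7% / 82.4% | 75.0% / 93.2% |
| 25% | 21.8% / 51.3% | 32.8% / 64.4% | 54.6% / 82.3% |
| 20% | 8.5% / 28.8% | 15.0% / 41.2% | 32.0% / 63.5% |

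With the nine-comparison correction, no cell reaches 80%.

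**The case against.** Several stronger readings are tempting, and the document does not support them.

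- **That 30% is an upper limit for the placebo arms.** The effectiveness statement concerns stopping caries damage, whereas the 30% is a complication rate. The source children had no additional treatment, which leaves open some routine advice. The Participants section also admits children arriving with acute pain or infection, whose rate may be higher. Clinic cards and the 12-month pain and abscess history may also count events differently.
- **That 10% is optimistic because the active arms do not receive conventional treatment.** The different source does not show which way the figure errs. The Protocol's introduction says that operative treatment often fails, and Risks 1a says that earlier studies point to lower rates. Those sources are not at hand.
- **That power must fall.** The same advice goes to every arm and 10% is stated as a ceiling, so the active rate may fall too. If the full 20-point gap survives (25% vs 5%), power rises. If the risk ratio is what stays constant, power falls.
- **That Risks 1a simply tells the team a shortfall is acceptable.** Its sentence is conditional on a treatment rate below 10%, and a larger difference does need fewer patients.

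These objections limit the size and certainty of the point but do not remove it. The mismatch between the source of the 30% and the care in the placebo arms remains, and the word conservative is argued from one arm only. The condition in Risks 1a must also be met by a wide margin before even 49 completers suffice.

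**Conclusion.** The point stands in a limited form. The planning difference uses a control rate from children without the care given to all arms, makes no allowance for that care, and is labelled conservative on a one-sided argument. The 30% may overstate the placebo rate; by how much, and how much power is lost, cannot be derived from the document. Over the assumed pairs of rates, power with 98 per group runs from 51% to 91%, against 80% as planned.

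A reader might take the 41% at 49 per group as the cost of the placebo-rate assumption. It is not: it arises at 30% vs 10%, because the plan's formula gives 98 and not 49. It does mean that the 80% claim fails for the planned completers before the placebo rate is questioned (72% even with no multiplicity correction), and that there is no margin to support the reassurance in Risks 1a. The figures rest on the Fig 1 formulas, alpha 0.05 and nine comparisons unless stated otherwise.

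**What to change.** 1. **Risks, 1a:** delete the description of the assumptions as conservative and the statement that power can be achieved with fewer patients.
2. **Sample size calculation:** state that the 30% comes from children without the advice and toothpaste recommendation given to all arms, and that it may therefore overstate the placebo rate. Do not call it an upper limit.
3. **Sample size calculation:** replace the 80% claim with a two-way power table for 49 completers per group, with placebo at 20%, 25% and 30% and active from 5% to 10%, marking every pair other than 30% vs 10% as an assumption. The table in step 4 of the working can serve.

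The cost is wording and a short table, and the stated power becomes less favourable. The fix requires no extra patients.

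### The protocol's own formula requires 98 children per group, not 49; with 49, power for one placebo-versus-active comparison is about 41%, not 80%

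*Protocol*

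**What the plan says.** The Sample size calculation section expects complications in 30% of placebo children and at most 10% of treated children. It sets the multiplicity count by stating that "the planned number of various proportions for comparison will be 9", and concludes that "for the study we need 49 children in each group" "with α error 0.05 and with a study capacity of 80" per cent. Six groups of 49 make 294, raised to 70 per group (420) for losses.

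Fig 1 prints a sample size formula with a two-sided critical value at α/(2τ), and a power formula. Its legend defines "n = the sample size (for one comparison, therefore two equivalent groups").

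The Risks section relies on the same figure. Item 1a says the "sample size calculation was estimated using conservative assumptions" and that, should the treatment-group rate prove lower than 10%, "statistical power can be achieved even with a lower number of patients". Item 1b plans 70 per group so that "there are still at least 49 in every group at the end of the project", assuming 30% loss. Risk 2a accepts excluding doubtful cases from analysis on the ground that the extra enrolment protects power.

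**The concern.** The section gives every input and both formulas, so the figure of 49 can be checked directly, and it does not come out. The legend can be read as making n the total over the two groups of a comparison. The power formula beside it makes n the size of each group. The two readings differ by a factor of two.

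This is the protocol's only justification of its size. If 49 is half of what the method requires, a placebo-versus-active comparison with the expected effect fully present would miss significance more often than not. A non-significant result could then be taken as evidence of no effect by a reader who trusts the stated 80%. The Risks section would also be tolerating under-recruitment and exclusions against a power reserve that does not exist.

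**Working it through.** **Inputs**, all from the Sample size calculation section except the loss rate:
- p_A = 0.30 (placebo) and p_B = 0.10 (treatment)
- α = 0.05 with τ = 9 comparisons, two-sided in Fig 1
- power 80%
- loss 30% (Risks, item 1b)

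**Sample size by the first formula in Fig 1**
- Variance term: 0.30 × 0.70 + 0.10 × 0.90 = 0.21 + 0.09 = 0.30
- Divided by the squared difference: 0.30 / 0.20² = 7.5
- z at 1 − 0.05/18 = 2.7729; z at 0.80 = 0.8416; sum = 3.6145
- n = 7.5 × 3.6145² = **97.99, so 98**

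**Reproducing the printed figure.** 97.99 / 2 = 48.99, which rounds to 49. The loss step is consistent: 49 / 0.70 = 70.

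**What n means.** The second formula in Fig 1 sets z = (p_A − p_B) / √[p_A(1 − p_A)/n + p_B(1 − p_B)/n]. Each group's variance is divided by n, so n is the size of one group.

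**Power by the second formula, 30% against 10%** (the second Φ term is negligible)

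| Evaluable per group | Critical value | z | Power |
|---|---|---|---|
| 49 | 2.773 (τ = 9) | 0.20/√(0.30/49) = 2.556 | 41.4% |
| 70 (no loss) | 2.773 (τ = 9) | 3.055 | 61.1% |
| 98 | 2.773 (τ = 9) | 3.615 | 80.0% |
| 49 | 1.960 (τ = 1) | 2.556 | 72.4% |

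The formula returns 80% at 98 per group, which confirms the per-group reading.

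**Other methods.** With τ = 9 and 80% power, the required size per group is 86 one-sided, 99 by arcsine, 103 with pooled variance and 113 with pooled variance and continuity correction. With no multiplicity correction, the printed two-sided formula gives 59. A one-sided, pooled-variance test without correction does give 49, but that is not the method printed.

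**Implied requirement on the stated inputs.** 98 × 6 = 588 evaluable. With 30% loss, 98 / 0.70 = 140 per group and 140 × 6 = 840.

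**What 49 per group can detect at τ = 9**
- 40% against 10%: power 81%
- 30% against 4%: power 81% (formula n = 48.0)
- 30% against 5%: power 75% (formula n = 53.8, so 54)

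**Sensitivity to the placebo rate.** The protocol gives no rate other than 30%; those below are assumptions for illustration. With 49 per group, τ = 9 and 10% under treatment, a placebo rate of 25% gives 22% power and a rate of 20% gives 8.5%.

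**The case against.** The strongest points on the other side limit the claim without removing it.

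- **The halving is not documented.** The legend is loosely worded and no division by two appears. That stands, so the origin of 49 is an inference. The conclusion does not depend on it: 49 in the printed power formula does not give 80%, however it arose.
- **The 41% is specific.** It is the power of one placebo-versus-active comparison of 30% against 10% at 0.05/9 with 49 evaluable. A reader might infer that every pairwise comparison has 41% power. The documents do not support that, because the 30% and 10% are expected only for placebo and treatment groups; comparisons between products or between schedules were not sized on this difference.
- **Risks item 1a is conditional.** It says fewer patients could suffice if the treatment rate falls below 10%. A reader might call that simply false, but at 30% against 3% the formula asks for 43 per group. The sentence can be true; its starting point is wrong, because a rate of about 4% is needed merely to justify 49.
- **The placebo rate is a separate matter.** The 30% comes from waiting-list children given no additional treatment, whereas all trial groups receive advice and a recommendation to use fluoride toothpaste, an approach the Interventions section regards as effective. A reader might infer that the true placebo rate is known to be lower, or that toothpaste is supplied. The protocol says neither.
- **Pooling schedules.** Two groups of 49 make 98, so pooling may look like a rescue at no cost. The WP4 primary aim asks about both the method and the application protocol. Pooling would change that question and the number of comparisons: three pooled arms have three pairwise comparisons, for which the formula gives 79, so the match with 98 is partly coincidence.

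**Conclusion.** The stated figure is wrong as written. On the protocol's own inputs and formulas, 80% power needs 98 evaluable children per group, twice the 49 stated. At 49 the power for one placebo-versus-active comparison is about 41%, and no loss to follow-up (61%) or no multiplicity correction (72%) would bring it to 80%.

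This rests on the protocol's normal-approximation formula with 30% against 10%, two-sided testing and τ = 9. At 49 per group, pooled variance (38%) or Fisher's exact test (30%) gives lower power. A separate analysis plan would not cure the point, because the protocol itself states the figure. The description of the assumptions as conservative is not supported, and neither under-recruitment nor further exclusions can be defended by assured power.

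**What to change.** 1. In the Fig 1 legend, define n as the number of children in each group.
2. Replace the 80% claim with: 49 evaluable per group give about 41% power for one placebo-versus-active comparison of 30% against 10% at 0.05/9. Alternatively, state the difference detectable with about 80% power: 10% against about 40%, or 30% against about 4%.
3. In Risks item 1a, withdraw the description of the assumptions as conservative. Requalify the sentence on fewer patients: even 49 per group reaches 80% only if the treatment rate is about 4% against 30%. Remove the reliance on assured power in risk 2a.
4. Optionally, show power for lower placebo rates, labelled as assumptions (25%: 22%; 20%: 8.5%).

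The cost is a change of wording and a less favourable stated power; no extra patients are required. Keeping the 80% claim on the present inputs would instead require 588 evaluable children, or 840 enrolled at 30% loss. Pooling the two schedules is not part of this fix.
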